5.3 Expected Risks

5.3.1 Physical Harm: The risk of physical injury related to increasing physical activity in sedentary individuals is low. Similar trials have been conducted in high-risk coronary artery disease patients without adverse events. Patients with untreated cardiac symptoms (angina, palpitations) or poorly controlled pulmonary comorbidities (such as COPD or asthma) will be excluded. There is a potential for musculoskeletal or joint injury with increased physical activity. However, there are no reported injuries in multiple large randomized trials (29-31).

5.3.2 Blood Drawing: Patients will need to undergo blood draws at baseline and post-intervention. Risks to blood draws are minimal and include pain and discomfort, infection and hematoma/bruising. Thus, women have little increased risk secondary to blood collection. Blood work will be obtained by trained staff trained hospital staff at the time of clinic visits.

5.3.3 Urine Collection: Patients will need to undergo urine collection at baseline and post-intervention. Risks to urine collection are minimal and include a small risk of infection. Thus, women have little increased risk secondary to urine collection.

5.3.4 Breach of Confidentiality: The major risk to participants included in this study is data security and confidentiality. Data will be stored in a secure, password-protected server accessible solely to trained study staff. The Study Coordinator will be trained and certified in research ethics and HIPAA tenets. All data and specimens will be given a unique research ID that will be blinded to investigators with the exception of the Study Coordinator, who will function as an honest broker. UNC CHART does not contain any identifying information, subjects are identified through study ID. Subjects must log on to UNC CHART to receive message, UNC CHART will not have email or smart phone contact information.

5.4 Removal of Patients from Protocol

Patients will be removed from the protocol if musculoskeletal injury is incurred. Patient will also be removed from the protocol at patient request. The patients will receive a phone call following week 1 to assess for adverse events, but will not be contacted in weeks 2-12 to minimize bias from the Hawthorne effect of repetitive phone calls while on trial. Patients will be instructed to contact study personnel if any concern for injury or adverse event related to trial enrollment and be removed from study.

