1.0 BACKGROUND AND RATIONALE

1.1 Study Synopsis

Overweight and obese endometrial cancer (EC) survivors at UNC-CH will be approached for tailored feedback fitness intervention. We aim to enroll 36 evaluable women (18 in each arm) to evaluate if receipt of weekly tailored feedback messages can improve physical activity in EC survivors. We anticipate enrolling 39 participants to be able to evaluate 36. We hypothesize women receiving the feedback message intervention will increase step counts from baseline more than 2,000 steps compared to women in the non-intervention arm.

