8.2 Sample Size and Accrual

Prior studies and systematic reviews have shown participant standard deviations in daily steps of approximately 1300-1800 steps/day (20, 30, 32). Furthermore, previous studies measuring the impact of similar interventions on patient fitness levels have observed a patient step count change score standard deviation of approximately 1700 steps/day (29), where change score is defined as the change in step count from baseline to a particular week post-baseline. To determine whether there is a significant increase in physical activity among patients receiving the feedback messaging intervention versus those that do not receive the intervention, we will compare participant change scores between the each arm in our study. Assuming a participant change score standard deviation of 1800 steps/day, we estimate that 15 women will provide 80% power to detect a 2000-step difference in change score between arms (30), utilizing a two-sided Wilcoxon Two-Sample test with an alpha of 0.05. Within each arm, we will have sufficient power with $n = 15$ subjects to determine whether change scores within an arm are significantly different from zero, and we estimate that we will have >95% power to detect a change score of at least 2000 steps/day using a two-sided Wilcoxon Signed Rank test, assuming an alpha of 0.05 and a patient change score standard deviation of 1800 steps/day. We will also perform similar tests utilizing change scores computed at 4 weeks and 8 weeks post-baseline to determine whether these effects appear earlier on during the intervention period. We will also directly examine linear trends in daily step count with respect to time in days, as well as the overall three month average change in step count from baseline, via linear mixed models. Prior similar fitness intervention noted a 5% attrition rate in a large trial over 6 months time (29). To make a conservative estimate we will allow for 20% attrition and thus aim to enroll 39 total patients to obtain 36 evaluable datasets (18 patients in each arm). All power calculations were computing using G*Power software version 3.1.9.2 (33).

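### Section 5.4 takes injured women out of the study without keeping their later step counts, which can tilt the week-12 comparison towards the feedback arm

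*Combined protocol and SAP*

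**What the plan says.** Section 5.4 contains two removal rules. The first is "Patients will be removed from the protocol if musculoskeletal injury is incurred". The second tells women to "contact study personnel if any concern for injury or adverse event related to trial enrollment and be removed from study". One speaks of the protocol and the other of the study. Neither says whether the tracker data are still collected and used afterwards. Apart from the call after week 1, women "will not be contacted in weeks 2-12 to minimize bias from the Hawthorne effect", so between that call and the week-13 visit a removal depends on the woman reporting the problem herself.

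On risk, section 5.3.1 says "There is a potential for musculoskeletal or joint injury with increased physical activity". It also calls the risk low and adds that "there are no reported injuries in multiple large randomized trials".

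On analysis, section 8.3 compares the change from the baseline week to week 12 between arms with a Wilcoxon two-sample test. It takes the week-12 value from a participant's last week on study. Section 8.2 plans to "aim to enroll 39 total patients to obtain 36 evaluable datasets (18 patients in each arm)". The term evaluable is not defined anywhere. There is no statement that all randomised women are analysed by assigned arm, no rule for a missing week-12 value and no sensitivity analysis. Linear mixed models are planned in 8.2, but not as the primary analysis.

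**The concern.** Removal here is not plainly unrelated to arm or outcome. Section 1.1 hypothesises that women receiving feedback "will increase step counts from baseline more than 2,000 steps compared to women in the non-intervention arm", and in Appendix 1 a woman who reaches at least 90% of her step goal has the next goal set 500 steps above her weekly average, up to 12,000. If injury follows from extra walking, injuries should fall more often in the feedback arm. An injured woman is also likely to walk less for a time. If her later counts are left out, the comparison moves towards the effect in women who stayed uninjured and hides part of what the messages did in the women randomised to them. In a trial of 39, one or two women in an arm are enough to matter.

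**Working it through.** **1. The plan's own figure.** Inputs from 8.2: difference 2000 steps/day, SD of change 1800, two-sided alpha 0.05, Wilcoxon two-sample test, 15 women (read as per arm).
- Standardised effect: 2000/1800 = 1.111.
- Effective n per arm, using the Wilcoxon efficiency 3/π for normal data: 15 × 0.955 = 14.32. Noncentrality: 1.111 × √(14.32/2) = 2.97.
- Power from the noncentral t: 81.7% at 15 per arm and 78.8% at 14. The stated 80% at 15 per arm reproduces.
- A 20% loss from 39 leaves 39 × 0.8 = 31.2 women, or 15 to 16 per arm, with 82% to 84% power. Lost precision is therefore not the main issue. The question is which women are lost.

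**2. Bias formula.** Let L be the drop in a woman's week-12 steps after injury, and qF and qC the removal rates in the feedback and control arms. Take L as equal in both arms, and injury as unrelated to the change a woman would otherwise have shown. With μF and μC the mean changes without injury:
- all randomised: (μF − qF·L) − (μC − qC·L)
- removed women left out: μF − μC
- bias = L × (qF − qC)

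**3. Numbers.** The documents give none of L, qF or qC, so all are assumptions. If 39 women split 20 and 19, then 5% of the feedback arm is one woman, 10% is two and 20% is four.

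| qF vs qC | L = 2000 | L = 4000 |
|---|---|---|
| 5% vs 5% | 0 | 0 |
| 5% vs 0% | +100 | +200 |
| 10% vs 0% | +200 | +400 |
| 20% vs 5% | +300 | +600 |
| 20% vs 0% | +400 | +800 |
| 5% vs 10% | −100 | −200 |

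Units are steps/day; plus favours feedback. A simulation (20 vs 19 women, SD 1800, 4000 runs per scenario) agreed with each entry to within about 16 steps. For scale, the standard error of the difference is 1800 × √(1/20 + 1/19) = 577 steps.

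**4. Effect on the test.** The same simulation set the true all-randomised mean difference to zero and counted significant Wilcoxon results favouring feedback:

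| Scenario | All women kept | Removed women left out |
|---|---|---|
| 5% vs 5%, L = 2000 | 2.3% | 2.1% |
| 5% vs 0%, L = 2000 | 2.2% | 3.3% |
| 10% vs 0%, L = 2000 | 2.9% | 5.3% |
| 10% vs 0%, L = 4000 | 3.5% | 9.3% |
| 20% vs 0%, L = 4000 | 3.5% | 22.0% |
| 5% vs 10%, L = 2000 | 2.3% | 1.6% |

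**5. The other reading of week 12.** Section 8.3 ties the value to the participant's last week on study. A removed woman might then be scored on her last week before removal. She would be counted, but her post-injury steps would still be absent.

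**The case against.** The strongest counter-argument is that the tilt is possible but not shown. The only evidence in the documents on injury frequency is that the risk is low and that the cited trials reported none. Section 5.4 removes for musculoskeletal injury in either arm, so background injuries need not differ by arm. If the messages change nothing, injury rates should be equal and there is no bias. An injury first disclosed at the week-13 visit leaves week-12 steps already recorded. At the smaller assumed rates the bias is well below the standard error. All of this stands and limits how far the point can be pressed.

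A reader might infer stronger statements that the documents do not support:
- **That the comparison is tilted.** This needs more removals in the feedback arm and lower steps after injury. Neither is documented, and the sign reverses if controls are removed more often.
- **That the primary test is restricted to evaluable women.** That term appears in the synopsis, schema and sample-size text. Section 8.3 states no such restriction; it leaves the analysis set open.
- **That any reported adverse event leads to removal.** The wording is "any concern for injury or adverse event related to trial enrollment and be removed from study", which for adverse events is narrower.
- **That the data would arrive anyway because the tracker syncs by itself.** Section 5.1 plans email reminders to sync, and the Appendix 1 messages repeatedly ask women to sync. Keeping the tracker does not mean that the study receives the counts.

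What survives is that 5.4 states a removal rule and nothing in the plan keeps post-injury steps in the week-12 comparison.

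**Conclusion.** The concern holds as a potential bias that the plan leaves open, with an expected direction but no known size. For removal-rate differences of 5 to 20 points towards feedback and losses of 2000 to 4000 steps, the range is +100 to +800 steps/day against a 2000-step target. Since 5.3.1 describes the risk as low, the lower end (one or two more removals in the feedback arm, +100 to +200 at a 2000-step loss) is the more relevant illustration. The figures rest on assumed rates and losses, an equal loss in both arms, and injury unrelated to a woman's underlying change. The change is worth making because it is cheap and removes the dependence on those unknowns for every woman who keeps syncing. Whether an injured woman should stop the walking programme is a clinical matter and is not judged here.

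**What to change.** Leave the clinical removal rule as it is, and change the following:
- **Section 5.4.** State that, unless consent is withdrawn, synced step counts continue to be collected through week 12 after removal, using the email sync reminders already planned. This is the core of the fix.
- **Section 8.3, analysis set.** State that all randomised women with week-12 data are compared in their assigned arm by the planned Wilcoxon test, and drop or define the term evaluable.
- **Section 8.3, week 12.** Fix the week by calendar time from baseline. If the baseline week is days 1 to 7, week 12 is days 78 (11 × 7 + 1) to 84 (12 × 7).
- **Reporting.** Give removals by arm and reason.
- **Missing week-12 counts.** Prespecify two sensitivity analyses: the planned linear mixed model, and a Wilcoxon test giving removed women without data an unfavourable value, for example the worst rank. The mixed model should not become primary. For a woman who stops syncing it sees only pre-injury steps, so it cannot recover the loss, and it would displace the test on which the stated power rests.

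The cost is a few sentences and, if needed, a consent line. The consent form was not available here, so check whether it already covers data after removal. A small downside is that some removed women will not sync, so some data will stay missing.

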6.0 TIME AND EVENTS TABLE

6.1 Time and Events Table

	Baseline visit	Week 1	Week 2-12	Follow up visit (Week 13)
Inclusion/Exclusion Criteria	X			
Informed Consent	X			
Education on fitness tracker and CHART	X			
Blood draw for fasting glucose, insulin, LDL	X			X
Blood and urine for banking	X			X
Fitness tracker daily step count monitoring		X (Baseline)	X	X
Weekly messages			X ¹	
AE Assessment		X (Phone call)		X (in person)
FACT-G ²	X			X
Baseline survey including GPAQ ³	X			
Measurements: Weight, Height, Waist/Hip Ratio	X			X
Completion survey				X ¹

¹Only patients in the tailored feedback message arm will receive weekly messages in weeks 2-12 and complete the completion survey.

²Functional Assessment of Cancer Therapy, version 4 scale will be used to evaluate quality of life.

³Global Physical Activity Questionnaire, version 2 will be used to assess baseline physical activity.

7.0 UNANTICIPATED PROBLEMS

7.1 Definition

As defined by UNC's IRB, unanticipated problems involving risks to study subjects or others (UPIRSO) refers to any incident, experience, or outcome that:

- Is unexpected (in terms of nature, severity, or frequency) given (a) the research procedures that are described in the protocol-related documents, such as the IRB-approved research protocol and informed consent document; and (b) the characteristics of the subject population being studied;
- Is related or possibly related to a subject's participation in the research; and
- Suggests that the research places subjects or others at a greater risk of harm (including physical, psychological, economic, or social harm) related to the research than was previously known or recognized.

7.2 Reporting

Any UPIRSO that occurs during the conduct of this study and that meets all three criteria listed in 6.1 must be reported to the UNC IRB using the IRB's web-based reporting system.

8.0 STATISTICAL CONSIDERATIONS

8.1 Study Design

This is a randomized, single-center, tailored feedback message intervention trial. The project will use fitness trackers to measure increase in physical activity from baseline in women randomized to receive weekly motivational feedback messages. A control group will receive a fitness tracker but no feedback message reinforcement. The primary objective of the study is to detect a 2,000 mean daily step increase from baseline in patients undergoing the feedback message intervention. Therefore, patients will be randomized, 1:1 using a 6-block scheme.

Exploratory objectives include gathering data on the acceptability of the intervention, as well as desired frequency, timing, and content of messages for use in a larger trial. Additionally, outcomes that will be the goal of a larger trial will be explored. These endpoints include: BMI, waist/hip ratio, QOL as measured by FACT-G, and serum metabolic markers (fasting insulin, glucose, and LDL).

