5.1 Duration of Study

Patients enrolled in this study will participate for approximately 12 weeks. The participants will be consented at the end of their cancer treatment. The participant will remain on study until their next clinic visit (~3 months).

There will be up to three in-person interactions with the patients in this study: during a clinic visit where the study is introduced, on the day of the baseline visit, and at the time of their 3-month follow up or post-intervention visit. Patients will be approached by the study coordinator for participation in this study during routine clinic visits. If a provider identifies eligible patients in advance of their scheduled visit and notifies the study coordinator, the study coordinator will contact the patient via telephone prior to their clinic visit to introduce the study and assess interest. If the patient is interested, the study coordinator will obtain a telephone consent. At the next scheduled visit, the study coordinator will obtain the patient's signed consent and provide a physical hardcopy of their signed consent form to the patient prior to initiating any study activities.

There will also be three phone calls from the study team: prior to the baseline visit to remind the patient to fast for blood collection, at the end of week 1 to ensure successful use of the fitness tracker, and prior to the post-intervention visit to remind the patient to fast again. For all subjects, study staff plans to send out email reminders so they can sync their Fitbits in time and log into UNC CHART to ensure data quality.

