After the above measurements and vitals are taken, patients will complete an enrollment survey including the GPAQ survey to measure baseline activity and baseline FACT-G assessment (27, 28). Pre-intervention FACT-G total score and sub-scale scores (physical well-being, social well-being, emotional well-being and functional well-being) will be compared to post-intervention scores. Finally, baseline fasting glucose, insulin and LDL will be obtained at the time of study baseline activities. Blood and urine will be collected and stored for potential future metabolomic profiling. Patients will then be randomized to either receive or not receive tailored feedback messages through UNC CHART. Participants randomized to the message arm will begin receiving encouragement and reminder UNC CHART messages to increase physical activity weekly based on the CHART algorithm (Appendix 1). Participants on the feedback arm will receive 1 message per week during the 3-month study period.

For the first week after initiating the study, each patient's baseline step count will be obtained from the fitness tracker. The mean step count over these 7 days will represent the patient's baseline step count. After the baseline week is completed, the study team will contact patients to ensure successful use of technology.

At the time of next follow up visit, the patient will undergo repeat weight, height, waist circumference, and hip circumference assessment. Heart rate and blood pressure will also be recorded at the follow up visit. The patient will complete a post-intervention acceptability survey and complete a post-intervention FACT-G assessment. Post-intervention fasting glucose, insulin, and LDL will be performed. Urine and blood will also be banked via the Tissue Procurement Facility (TPF) at the Lineberger Comprehensive Cancer Center (LCCC) for future metabolomic profiling.

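### The protocol discloses a block size of 6 and describes no allocation concealment, so up to 9 of 39 allocations could be deduced by a recruiter who sees earlier assignments

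*Combined protocol and SAP*

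**What the plan says.** Section 8.1 describes the design: "This is a randomized, single-center, tailored feedback message intervention trial". It then says that "patients will be randomized, 1:1 using a 6-block scheme". No variation in block size and no stratification is described, so a single list serves all 39 women (36 evaluable, 18 per arm; section 8.2).

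On recruitment, section 5.1 says: "Patients will be approached by the study coordinator for participation in this study during routine clinic visits". Women identified in advance are telephoned by the same role: "If the patient is interested, the study coordinator will obtain a telephone consent".

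On order of events, section 5.2 places randomisation after the baseline measurements, surveys and blood draw: "Patients will then be randomized to either receive or not receive tailored feedback messages through UNC CHART". Section 9.3 requires registration in OnCore.

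On visibility of the arm, the control group gets a tracker but no messages (section 8.1). Under the table in section 6.1, only the message arm gets weekly messages in weeks 2 to 12 and fills in the completion survey.

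The protocol does not say who generates the list, who holds it, how an allocation is released, or which staff are masked.

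**The concern.** Within a block of known size, each assignment narrows what can follow, and the last is always determined. A recruiter who has seen the earlier assignments can therefore anticipate some of the later ones.

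There is room to act on this. Women are eligible for up to six months after therapy and are seen about every three months, so an approach can sometimes be deferred. Entry also depends on the treating physician's approval and on a judgement-based exclusion (sections 3.1 and 3.2). Allocating after consent does not fully close the gap, because a prediction may already exist while enrolment is still discretionary.

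If more motivated women entered when the message arm was expected, the primary contrast would be biased. That contrast is an unadjusted Wilcoxon comparison of change in steps (section 8.3). No measure of motivation is planned, so later adjustment could not be relied on to repair it.

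This is more than a missing detail: the plan names a method and prints the parameter that makes it predictable.

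**Working it through.** **Plan's own figure.** The documents give no figure for predictability, so there is none to reproduce. (The sample size behind the design does reproduce: with a 2,000-step difference, SD 1,800 and two-sided alpha 0.05, a simulated Wilcoxon test has 80.4% power at 15 per arm, reading the plan's 15 women as per arm.)

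**Inputs.** Ratio 1:1 and block of 6, so 3 + 3 (section 8.1). If the phrase were read as six blocks, the 36 evaluable women would again give blocks of 6. Total 39 (section 8.2), which is 6 full blocks plus 3 women.

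**Conditions assumed for the upper bound.** The recruiter knows the block size, sees every earlier assignment, and has no other woman awaiting allocation.

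**Certain allocations.** A block has C(6,3) = 20 equally likely sequences. An allocation is certain once one arm's three places are used.
- Positions 1 to 3: 0.
- Position 4: the first three are all one arm, 2/20 = 0.10.
- Position 5: the first four contain three of one arm, 2 × C(4,3)/20 = 8/20 = 0.40.
- Position 6: 1.00.
- Sum: 1.5 of 6 = 25%.
- Over 39 women: 6 × 1.5 + 3 × 0 = 9.0, and 9.0/39 = 23.1%.

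**Best guess** (always guess the arm with more places left; toss a coin if level). Success by position is 0.5, 0.6, 0.6, 0.7, 0.7, 1.0, which sums to 4.1 of 6 (68.3%). Over 39 women: 6 × 4.1 + (0.5 + 0.6 + 0.6) = 26.3, or 67.4%. Chance alone gives 19.5.

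**Relaxing the conditions** (certain share of a full block):

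| Situation | Certain share |
|---|---|
| All earlier assignments seen, none pending | 25.0% |
| One other woman pending | 0.5/6 = 8.3% |
| Two others pending | 0.1/6 = 1.7% |
| Each earlier assignment seen with probability 0.9 | 18.2% |
| Seen with probability 0.75 | 10.5% |
| Seen with probability 0.5 | 3.1% |

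Over 39 women, one pending gives 6 × 0.5 = 3.0 certain allocations (7.7%).

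**Effect of varying block sizes.** Take sizes drawn at random from 4 and 6, with the recruiter knowing the possible sizes but not their order. By simulation, about 5.5% of allocations are certain (0.055 × 39 = about 2), but best-guess success is about 26.8 of 39. That is no lower than the 26.3 for a fixed block of 6.

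**What predictability could mean for the contrast** (illustration only). Suppose a recruiter always follows the best guess and enrols women whose expected change is e steps/day above average when the message arm is expected, and e below when control is expected. The bias in the arm difference is 2 × (2 × 26.3/39 − 1) × e = 0.70e. For an assumed e of 250 to 900, that is about 175 to 630 steps/day, or 9% to 31% of the 2,000-step target. The documents give no value for e, and nothing in them suggests that this happened.

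**The case against.** The strongest reply is that the conditions for the upper bound are not in the documents. No passage says that the coordinator sees allocations. Both arms get the tracker, CHART training, reminder emails and the week-1 call. Messages are read by logging in to CHART under a study ID, and section 5.4 rules out contact calls in weeks 2 to 12. The first documented step that must reveal the arm to staff is the completion survey at week 13. Also, a woman approached by telephone or at an earlier visit may not be the next one randomised. All this stands, and it is why the figures are upper bounds.

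Four stronger readings are tempting, but the documents do not support them.
- A reader might infer that a quarter of allocations are known before a woman is approached. Randomisation follows consent and baseline tests, and the share at approach drops quickly when others are pending.
- A reader might take section 5.3.4, where research IDs are "blinded to investigators with the exception of the Study Coordinator, who will function as an honest broker", as evidence that the coordinator is unmasked. That text is about confidentiality of data and specimens, not allocation.
- A reader might infer that one person recruits everyone. The text names a role, and providers also identify patients.
- A reader might call the trial open-label. The protocol does not use the term. Only the participants' awareness of their arm is clear, and masking of staff is not described.

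It can also be said that a block of 6 is conventional in a small pilot and matters little if allocation is well concealed. That is fair, but no concealment is described. Selection would also have to track future change in steps, not just activity level, to bias this endpoint. That limits the likely size of the bias without removing the risk.

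**Conclusion.** The point holds as a conditional weakness of the stated method. A disclosed block of 6, a single list, participants who cannot be masked, a recruiting role that also takes consent, and no described concealment together leave up to 9 of 39 allocations (23%) deducible and about 26 of 39 guessable. These maxima assume a known block size, full sight of earlier assignments and nobody pending; the certain share is about 8% with one woman pending. The documents neither establish nor exclude those conditions. The size of any resulting bias is unknown, and no misuse is implied. The change is worth making because it is cheap and because this pilot is meant to lead to a larger randomised trial, which could inherit the method.

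**What to change.** For allocations not yet made, replace the wording in section 8.1 with permuted blocks of randomly varying size, and keep the sizes in a document that recruiting staff do not see. State in the protocol that:
- a statistician outside recruitment generates and holds the list;
- each allocation is released only after registration and completion of the baseline-visit measures, which makes enforceable the order that section 5.2 already implies;
- past assignments are kept from recruiting staff as far as feasible, and which staff know the arm.

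The independent holder and the restriction on past assignments are essential. Varying the sizes mainly removes certainty and does not lower best-guess success.

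The cost is a new list, a wording change and a named list-holder. The possible arm imbalance changes slightly. At present 39 is not a multiple of 6, so the arms can differ by up to 3. Blocks of 4 and 6 have the same limit, provided the change is made at the end of a current block rather than part-way through one. Amendment 3 raises accrual because some participants did not complete, which suggests enrolment is well advanced. Few allocations may be left to change, and the main benefit may be to the larger trial.
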